### 5.4. FULL ANALYSIS SET

Each DB treatment period will have a Full Analysis Set (FAS). The Full Analysis Set 1 (FAS1) will include all randomized subjects who took at least one dose of study drug during the DB1 treatment period and have at least one post-baseline efficacy time point assessment for either pain or symptom (among nausea, photophobia, phonophobia) in DB1. The Full Analysis Set 2 (FAS2) will include all re-randomized subjects who took at least one dose of study drug during the DB2 treatment period and have at least one post-baseline efficacy time point assessment for either pain or symptom (among nausea, photophobia, phonophobia). Subjects in the DB1 will be analyzed according to their randomized treatment. Subjects in the DB2 will be analyzed according to their re-randomized treatment. The FAS1 and FAS2 will be used for all analyses of efficacy endpoints.

### 5.5. PER PROTOCOL SET

The Per Protocol Set (PPS) will include all FAS1 subjects who have at least 1 post-baseline primary endpoint assessment for both co-primary endpoints (observed and LOCF), and who have no significant protocol deviations that will impact the collection

or interpretation of the co-primary endpoint data during the DB1 treatment period. Identification of subjects in the PPS will be determined before the database lock and unblinding. Subjects in the PPS will be analyzed according to their DB1 randomized treatment.

## 5.6. PROTOCOL DEVIATIONS

Protocol deviations will be captured during monitoring visits or via remote monitoring. All deviations will be recorded in the [REDACTED] clinical trial management system and will be categorized as major or minor. Major protocol deviations will be summarized by deviation type using frequency counts. All deviations will be listed by subject.

## 6. GENERAL ASPECTS FOR STATISTICAL ANALYSIS

### 6.1. GENERAL METHODS

#### 6.1.1. Summary Statistics

In general, descriptive statistical methods will be used to summarize the data from this study. With appropriate sample sizes, hypothesis testing can be performed for the co-primary and secondary efficacy endpoints.

The term “treatment group” refers to the applied treatment regimen during DB1 or DB2 (DFN-15 120 mg or placebo). All data collected during the study will be included in subject data listings. All subjects entered into the database will be included in subject data listings. Unless otherwise noted, the data will be sorted first by treatment group, subject number, and then by date within each subject number.

Unless stated otherwise, the term “descriptive statistics” refers to number of subjects (n), mean, median, standard deviation, minimum, and maximum for continuous data and frequencies and percentages for categorical data.

All categorical/qualitative data will be presented using absolute frequency counts and percentages. The total number of subjects in the treatment group overall (N) in the specified population will be used as the denominator for percentage calculations, unless stated otherwise in the table shell. All percentages will be presented in parentheses with 1 decimal point, unless otherwise specified. Percentages equal to 100 will be presented as 100% and percentages will not be presented for zero frequencies.

Unless specified otherwise, all statistical testing and confidence intervals (CIs) will be 2-sided and will be performed using a significance (alpha) level of 0.05.

### 6.1.2. Reporting Precision

Summary statistics will be presented to the following degree of precision:

**Table 3 Reporting Precision**

Statistics	Degree of Precision
Mean (of all kinds), Median, Quartiles, Confidence limit boundaries	One more decimal place than the raw data
Standard deviation, Standard error	Two more decimal places than the raw data
Minimum, Maximum	The same number of decimal places as the raw data
P-value	Rounded to 3 decimal places and formatted as 0.xxx; P-values smaller than 0.001 as '<0.001'; P-values smaller than 0.0001 as '<0.0001'
Percent	One decimal place

All fractional numeric values will be presented with a zero to the left of the decimal point (for example, 0.12 - 0.30, not .12 - .30).

All analyses and summaries will be produced using Statistical Analysis System (SAS®) for Windows, Release 9.3 (SAS® Institute Inc., Cary, NC, USA) or higher. Summaries will be presented by treatment unless otherwise specified.

## 6.2. KEY DEFINITIONS

### 6.2.1. Baseline

Unless specified otherwise, the baseline assessment will be the latest available valid measurement taken prior to the administration of the initial dose of study drug during each DB period. In the event that a migraine attack happens immediately following randomization, the assessments taken on the same day as the administration of the initial dose of study drug, but prior to the time study drug is taken, can be considered as baseline.

### 6.2.2. First Dose Date

The first dose date for DB1 is defined as the first dose of study drug taken after randomization in DB1. The first dose date for DB2 is defined as the first dose of DB2 study drug taken after re-randomization into DB2.

### 6.2.3. Study Day

If the assessment date is after the date of the first dose during each treatment period, the study day is calculated as date of assessment - date of the first dose administration + 1. If the assessment date is prior to the date of the first dose during each treatment period, the study day is calculated as date of assessment - date of the first dose administration. Study day 1 for each DB treatment period is the day during which the first dose of study drug during the first treatment period is administered.

### 6.2.4. Treatment Day

If the assessment date is after the date of the first dose during the current DB treatment period, the treatment day is calculated as date of assessment - date of the first dose administration during the current DB treatment period + 1. If the assessment date is prior to the date of the first dose during the current DB treatment period, the treatment day is calculated as date of assessment - date of the first dose administration during the current DB treatment period. Treatment day 1 is the day during which the first dose of study drug during the current DB treatment period is administered.

### 6.2.5. Treatment Emergent Adverse Events

A TEAE for DB1 is defined as an AE that started on or after the first dose of study drug (DFN-15 or placebo) in DB1 or any existing AE that worsens in severity on or after the date of the first dose of study drug in DB1 up to 5 days after the date of the last dose of study drug in DB1 or up to taking DB2 study drug, whichever occurs first.

A TEAE for DB2 is defined as an AE that started on or after the first dose of study drug (DFN-15 or placebo) in DB2 or any existing AE that worsens in severity on or after the date of the first dose of study drug in DB2, up to 5 days after the date of the last dose of study drug in DB2.

## 6.3. MISSING DATA

Subjects are allowed to withdraw from the study at any time. Subjects who withdraw from the study will have all data listed and, wherever relevant, included in any subject summaries. Analyses on quantitative and categorical variables will include data from subjects with non-missing values. Partial dates will be listed as recorded on the case report form (CRF). Imputation of missing or incomplete dates will only be performed for summaries of AEs and concomitant medications unless otherwise specified.

Partial Missing Start or Stop Date	Imputed Start Date	Imputed Stop Date
Missing month and day, and the year is present	January 1 of that year or DB period dose date if the year is the same as the year	December 31 of that year

Partial Missing Start or Stop Date	Imputed Start Date	Imputed Stop Date
	of the DB period dose date	
Missing day, but year and month are present	First day of that month or DB period dose date if the year and month are the same as the year and month of the DB period dose date	Last day of that month
Missing month, but year and day are present	Missing month imputed as January	Missing month imputed as December

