### 7.5.2. Prior and Concomitant Medications

All prior and concomitant medications will be classified using the Anatomical Therapeutic Chemical (ATC) classification and preferred drug names from the World Health Organization Drug Dictionary (WHO-DD), version March 2016.

Summaries of medications will be presented in tabular form using the highest level ATC term as an upper classification and the preferred drug name as a lower classification level. All medications will be summarized by treatment group and overall and sorted by descending counts in the upper classification term and the lower classification term within the upper. The summary will consist of the frequency and percentage of subjects who used the medication at least once. For each subject, the medication will be counted only once within the upper classification level and only once within the lower classification level.

Medications will be considered prior if stopped before the DB1 dose date. Medications with a start or stop date on or after the DB treatment period dosing date will be considered concomitant medications. If a concomitant medication starts on or after the start time of DB1 dose administration, it is considered a concomitant medication to the study treatment in DB1, but not in DB2. If a concomitant medication starts on or after the start time of DB2 dose administration, it is considered a concomitant medication to the study treatment in DB2. All medications marked as ongoing are concomitant medications. A medication with an incomplete start/stop date will have its date imputed as described in SAP Section 6.3 solely to determine if the medication is prior or concomitant.

Summaries of prior and of concomitant medications will be presented separately in tables and will be based on the SS. Prior and concomitant medications will be listed by subject. An identifier will be included to show if a medication is prior or if it is concomitant with respect to the applicable DB treatment period.

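### SAP 6.3 can impute an adverse event start later than its recorded stop, and does not say which dose applies when both the DB1 and DB2 doses match a partial date

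*SAP*

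**What the plan says.** The SAP 6.3 table has two rows that can move a partial start date to a dose date. With the day missing, the imputed start is "First day of that month or DB period dose date if the year and month are the same as the year and month" of the dose. With month and day missing, it is "January 1 of that year or DB period dose date if the year is the same as the year" of the dose. Neither row refers to the stop date. The section limits its own scope: "Imputation of missing or incomplete dates will only be performed for summaries of AEs and concomitant medications unless otherwise specified".

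SAP 6.2.5 classifies treatment-emergent adverse events (TEAEs) by date of start or worsening, one period at a time. For the first period, "A TEAE for DB1 is defined as an AE that started on or after the first dose of study drug" in DB1, and the window runs "up to 5 days after the date of the last dose of study drug in DB1 or up to taking DB2 study drug", whichever is earlier. For the second, "A TEAE for DB2 is defined as an AE that started on or after the first dose of study drug" in DB2, with its own 5-day limit. Neither definition tests the stop date.

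SAP 7.5.2 sends incomplete medication dates to 6.3 and then applies two rules: "Medications will be considered prior if stopped before the DB1 dose date", and "Medications with a start or stop date on or after the DB treatment period dosing date will be considered concomitant medications". It does not say which rule wins when a drug satisfies both.

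**The concern.** Moving a partial start to the dose date is a usual cautious convention when the event might have begun after dosing. It is not cautious when the record already shows that the event ended before dosing. The imputed start is then impossible, and a pre-dose event enters the TEAE tables. Pre-dose AEs will exist, because Protocol 9.2.2 collects AEs from consent.

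The second gap is that a subject can have two dose dates, one per period, and the table refers to the period's dose date without saying which one governs a record that matches both. Two programmers could follow the text and produce different tables.

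What is at stake is the proportion of subjects with TEAEs on DFN-15 and on placebo, which is the first secondary endpoint listed in Protocol 10.4.2 and SAP 4.2, and the prior/concomitant identifier promised in SAP 7.5.2.

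**Working it through.** The documents attach no figure to this rule, so there is nothing to reproduce. The check applies SAP 6.3, 6.2.5 and 7.5.2 literally to worked dates.

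**Inputs.** V3 is expected 2 to 7 days after the DB1 dose, and DB2 drug is to be used within 4 weeks of V3 (Protocol Table 9-1). The gap between doses is therefore about 2 days up to 7 + 28 = 35 days. The doses below, DB1 on 12 June 2017 and DB2 on 24 June 2017 (12 days apart), are illustrative.

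**Step 1: AE, start June 2017 with day missing, stop 5 June.** Year and month match the DB1 dose, so the imputed start is 12 June, 7 days after the recorded stop. It lies inside the DB1 window, so the event is a DB1 TEAE. If the rule is run again for DB2, the imputed start is 24 June and the event is also a DB2 TEAE.

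**Step 2: AE, same partial start, stop 18 June, between the doses.** For DB1 the imputed start of 12 June is possible, and the event is a DB1 TEAE. Run for DB2, the start becomes 24 June, 6 days after the stop, and the event is a DB2 TEAE too.

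**Step 3: as step 1, but DB2 dose on 3 July.** The month no longer matches DB2, so for that period the imputed start is 1 June. The event is a false TEAE in DB1 only.

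**Step 4: medication with the dates of step 1.** The stop of 5 June is before the DB1 dose, so the drug is prior. The imputed start of 12 June is on the dosing date, so it is also concomitant.

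**Step 5: how often both doses can match.** For doses d days apart, with the first equally likely on any day of a 365-day year, P(same month) = sum over months of max(0, days in month − d) / 365, and P(same year) = (365 − d) / 365.

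| Gap d (days) | Same month | Same year |
|---|---|---|
| 2 | 341/365 = 93% | 99.5% |
| 7 | 281/365 = 77% | 98% |
| 14 | 197/365 = 54% | 96% |
| 21 | 113/365 = 31% | 94% |
| 28 | 29/365 = 8% | 92% |
| 35 | 0% | 90% |

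These are chances that both doses fall in one month or year. They are not rates of affected records, and the documents give no distribution of gaps.

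**Step 6: two treatments for one event.** Allocation is 1:1 in each period (SAP 3.6). If the two randomisations are independent, which is an assumption, the treatments differ with probability 0.5 × 0.5 + 0.5 × 0.5 = 0.5.

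**Step 7: effect of a stop-date condition.** In steps 1 and 3 the event becomes a TEAE in neither period. In step 2 it is a TEAE in DB1 only. If the stop is missing or after both doses, the condition does not choose between the doses, so the SAP must also say which applies.

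**The case against.** Four points on the other side carry weight.

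First, a reader might infer that the SAP counts such events twice. The text does not say so. SAP 6.3 refers to a single dose date and never tells the programmer to impute one record twice, and the SAP 6.2.5 windows do not overlap, so one imputed start falls in at most one period. This stands: double counting needs the rule to be run per period, which the text neither requires nor excludes. What remains is that the dose is not named.

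Second, a reader might infer that drugs stopped before dosing become concomitant. They do not simply move, because SAP 7.5.2 also calls them prior. Protocol 10.5.6 counts a drug as concomitant only if taken between the first and last dose, and SAP section 11 lists no change to that. This points to prior as the intended answer, but the SAP wording leaves the conflict open, and Protocol 10.1 lets the SAP prevail.

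Third, exposure is limited. Sites record dates of first occurrence and resolution (Protocol 9.2.2.6), missing or inconsistent data are queried (Protocol 11.1.3), and screening lasts about 3 weeks. A year-only AE that stopped on 10 March with a dose on 12 June would need 94 days between its end and dosing. That exceeds 21 days of screening plus 28 days to treat (49 days), so it needs an extended screening period. Nor does the collection of neurological drugs from any past time (Protocol 8.5) imply many affected drug records: starts in earlier years are imputed within those years and never reach the dose-date rule.

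Fourth, the rule is the same for both arms, SAP 8.2.1 only summarises the TEAE proportion without naming a test, and partial dates are listed as recorded. A material dilution of the safety contrast is therefore not shown. None of this supplies the missing stop-date condition.

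**Conclusion.** The point holds as a defect of specification. As written, SAP 6.3 with 6.2.5 turns an AE recorded as ended before dosing into a TEAE with a start after its stop, whenever the partial start matches the dose month or year. This needs no assumption beyond a literal reading. For drugs the result is an unresolved dual classification. Counting one event in both periods is possible only if imputation is run per period and both doses match. It reaches two different treatments in about half of re-randomised subjects, assuming independent randomisations.

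The number of affected records cannot be derived from the documents and is probably small. The harm is impossible dates and wrong attribution in the safety tables. The co-primary analyses are not involved.

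**What to change.** Amend SAP 6.3 and 7.5.2 before unblinding:

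- **(a)** Use the dose date for a partial start only if the stop date is missing or on or after that dose. Never let an imputed start exceed a recorded stop.
- **(b)** Impute one start date per record and assign each AE to one period only. Name the dose that applies when both match, using the stop date and, where available, whether the AE was already recorded at V3. Do not default to DB1: AEs are reviewed at V3 (Protocol 9.2.1.3), so that default would charge to the DB1 treatment an event first reported at V4.
- **(c)** State that a medication with a stop date before the DB1 dose is prior only, whatever its imputed start.

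Items (a) and (c) cost a line each in the SAP and in the derivation program. Item (b) costs slightly more, because the visit of first report is not among the AE data items in Protocol 9.2.2.6. The SAP should therefore also state what is done when that visit cannot be established. No new data collection is needed.

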### **9.3. ADVERSE EVENTS**

All AEs will be coded using the Medical Dictionary for Regulatory Activities (MedDRA; version 19.0 or higher). Migraine headaches will not be captured as AEs. Migraine headaches will be captured by the subject in the eDiary provided to them, and the information will be entered into the appropriate eCRF page.

All AEs will be listed by subject. The following listings of AEs will be provided:

- All AEs
- Study-drug related AEs
- Serious adverse events (SAEs)
- AEs leading to death
- Adverse events leading to study-drug termination

Only TEAEs will be included in summary tables. Summaries for AEs will be presented for the SS, SS1, and SS2. An overall summary table of TEAEs will be produced for the following categories:

- Any TEAE
- Study-drug related TEAEs
- Serious TEAEs
- TEAEs leading to study-drug termination
- TEAEs leading to death

All TEAEs will be classified by system organ class (SOC) and preferred term (PT). Frequency count and the number of unique subjects of a TEAE will be tabulated by treatment(s) received. For the number of unique subjects reporting, if a subject reported more than one AE that was coded to the same SOC or PT, the subject will be counted only once for that specific SOC or PT.

The following summaries of TEAEs will also be provided:

- TEAEs by SOC and PT
- Study-drug related TEAEs by SOC and PT
- Serious TEAEs by SOC and PT
- TEAEs by maximum severity (mild, moderate, severe or missing) by SOC and PT
- TEAEs by strongest causality relationship (not related, possibly related, probably related, definitely related or missing) by SOC and PT

For TEAEs presented by relationship to study treatment(s), the strongest relationship to study treatment(s) during the study will be presented for each subject if coded to the same SOC or PT. For TEAEs presented by severity, the worst severity during the study will be presented for each subject if coded to the same SOC or PT. TEAEs with missing causality will be counted as related. TEAEs with missing severity will be counted as severe. The same will be true in the individual summaries.

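### SAP 6.3 gives an adverse event with only its month missing a January start, with no dose-date alternative, so a true TEAE arising in February to December drops out of the TEAE tables

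*SAP*

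**What the plan says.** SAP 6.3 (Missing Data) limits date imputation as follows: "Imputation of missing or incomplete dates will only be performed for summaries of AEs and concomitant medications unless otherwise specified". Its table has three start-date rows:

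- Month and day missing, year known: "January 1 of that year or DB period dose date if the year is the same as the year" of the double-blind period dose.
- Day missing, month and year known: "First day of that month or DB period dose date if the year and month are the same" as those of the dose.
- Month missing, day and year known: "Missing month imputed as January". Nothing in this row refers to the dose date.

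The imputed start then decides treatment emergence. In SAP 6.2.5, "A TEAE for DB1 is defined as an AE that started on or after the first dose of study drug" in that period, and the window runs "up to 5 days after the date of the last dose of study drug in DB1" or until DB2 drug is taken, if sooner. DB2 has a parallel definition. An existing event that worsens in the window also counts.

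SAP 9.3 states "Only TEAEs will be included in summary tables" and also "All AEs will be listed by subject". The proportion of subjects with a TEAE in each period is a secondary endpoint (SAP 4.2 and 8.2.1).

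**The concern.** The row with more date information is the only one without protection. An event known only by its year is counted as treatment-emergent if that year is the dosing year. Add the day of the month to the same record and it is sent to January, usually weeks or months before the dose.

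This runs against the SAP's own approach elsewhere. The two adjacent rows resolve uncertainty towards treatment emergence, and SAP 9.3 counts missing causality as related and missing severity as severe. At stake are the TEAE incidence tables and the TEAE secondary endpoint. No efficacy endpoint is involved.

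**Working it through.** The plan states no figure for this rule, so there is nothing to reproduce. The check applies the three start-date rows to known cases.

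**Inputs.** The start-date rows come from SAP 6.3. The window comes from SAP 6.2.5: an event is a TEAE if dose date ≤ imputed start ≤ dose date + 5 days.

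**One case.** Dose on 10 July 2017, true onset on 12 July 2017.

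| Part missing | Imputed start | TEAE? |
|---|---|---|
| Month only | 12 January 2017, 179 days before the dose | No |
| Month and day | 10 July 2017 | Yes |
| Day only | 10 July 2017 | Yes |

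**All 2017 dose dates.** Each of 365 dose dates is paired with true onset on days 0 to 5, giving 365 × 6 = 2190 true TEAEs.

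| Rule | Still TEAEs | Share |
|---|---|---|
| Month missing (January) | 186 | 186/2190 = 8.5% |
| Month and day missing | 2190 | 100% |
| Day missing | 2190 | 100% |

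The other 2190 − 186 = 2004 (91.5%) are placed before the dose. The 186 that survive are exactly the true January onsets: 171 with a January dose and 15 with a dose on 27 to 31 December. Every true TEAE with onset in February to December is lost from its own period.

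**A narrower calendar window.** Actual dosing dates are not in the documents. As an assumption, take doses from 9 May 2017 (the protocol version date given in SAP 11) to 8 November 2017 (the SAP signature date). That is 184 days × 6 = 1104 true TEAEs, of which the January rule keeps 0.

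**Plausibility of the imputed date.** Protocol 9.2.2.6 has sites record as adverse events only what started or worsened after consent. With about 3 weeks of screening and up to 4 weeks to treat in DB1 (Protocol 9.1), 31 January + 21 + 28 days = 21 March. Unless screening is extended, a January start for anyone dosed in DB1 after that date precedes consent.

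**The worsening limb.** This does not reliably rescue the event. Protocol 9.2.2.6 has a change in severity recorded as a separate event, which carries its own start date and so meets the same January rule.

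**Errors in the other direction.** With a dose on 5 January and a true onset on 8 March, the imputed start is 8 January. That is inside the 5 to 10 January window, so a non-TEAE is added. The enumeration above starts from true TEAEs and cannot show such cases.

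**Medications.** Under SAP 7.5.2 a medication is prior only if it stopped before the DB1 dose. It is concomitant if its start or its stop is on or after dosing, or if it is ongoing. Partial stop dates are imputed late. A January start therefore does not change the flag when the stop date is known or partial, or when the medication is ongoing. The same section limits imputed dates to that decision.

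**The case against.** The strongest reply is that the pattern will hardly occur. Participation lasts about 13 weeks, adverse events are reviewed at every visit, V3 and V4 follow each treated attack by 2 to 7 days, and missing data are queried to the investigator (Protocol 9.1, Table 9-1 and 11.1.3). With day and year known, few months are possible and a query should settle it. Nothing is hidden either, because all events are listed and SAP 6.3 lists partial dates as recorded. This stands as an argument about size. It does not justify a rule that gives the wrong answer whenever it is used.

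A second reply concerns the obvious remedy. Copying the dose-date alternative into this row discards the recorded day: an event on the 20th with a dose on the 10th would be placed on the 10th and counted, although the 20th lies outside the 5-day window. It could also turn screening events into TEAEs. This stands, and it shapes the fix.

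Three stronger readings are tempting, and the documents do not support them:

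- A reader might infer that the rule can only remove events. The January-dose example shows that it can add one.
- A reader might infer that every record with this pattern in the dosing year is misclassified. Collection starts at consent and the window is 5 days, so events that began in screening, or more than 5 days after the dose, are usually left out correctly. The loss applies to true TEAEs with onset after January.
- A reader might infer that medications are misclassified too. The prior or concomitant flag does not turn on the imputed start.

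**Conclusion.** The point holds as a minor but clear error in one row of SAP 6.3. A true TEAE with onset in February to December and only its month missing is imputed to January and leaves its period's TEAE tables and the TEAE secondary endpoint. The same event with only the year recorded would be counted. The usual direction is under-counting, against the SAP's own conservative conventions.

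Within the pattern the loss is large: 91.5% of true TEAEs over a full year of dose dates, and all of them if dosing fell between 9 May and 8 November 2017. Those shares assume evenly spread dose dates and onset days, and the second also assumes the calendar window. The documents do not say how many records will have this pattern. It is probably few, so the effect on reported TEAE rates is likely small. The priority is low.

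**What to change.** Amend the month-missing row before database lock. When the recorded year equals the year of the double-blind period dose, impute the start as the earliest date in that year that has the recorded day, is on or after that period's dose date, and is compatible with any known stop date and with adverse event collection from consent to end of study. Otherwise use January.

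For a true onset 0 to 5 days after the dose in the same year, that earliest date is the true onset, because a day number cannot repeat within six days. If onset crosses into the next year, the January fallback is correct. All 2190 enumerated cases are then kept.

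A simpler alternative, matching the adjacent rows, is the dose date itself unless a known stop date precedes dosing. It also keeps 2190 of 2190, but overrides the recorded day.

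Whichever is chosen, state which period's dose date applies when both doses fall in the same year, since TEAEs are counted by period. If the database holds the visit of first report, an event first reported by V3 cannot belong to DB2.

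The cost is one table row, one sentence on periods, and matching code. The downside is that some events that began before dosing may be counted as TEAEs, the same conservative direction as the adjacent rows. Keeping the recorded day limits this: a pre-dose event is miscounted only if its day number falls on one of the six window days, roughly 6/30 = 20% if recorded days are evenly spread and no stop date rules it out.
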